7.3.4. Study Population

The study population will include male PwSHA without a history of (or current) inhibitors to FVIII in Germany. Participants will be identified from the DHR (see Section 7.5.1 for further description of the DHR) and are expected to provide written informed consent to be included in this study. Participants will be captured in either the Roctavian or SoC Cohorts based on the treatment they receive during the study recruitment window. The study aims to enroll at least 67 PwSHA into the Roctavian Cohort and at least 330 PwSHA into the SoC Cohort. The therapeutic treatment strategy for an individual who consents to this study is made independently of the decision to participate in the study and enrollment into this study will not inform the treatment strategy.

Participants will be selected into one of two mutually exclusive Cohorts based on the treatment they receive for HA. The Roctavian Cohort will include participants who received Roctavian during the recruitment period. The index date for these participants will be the date Roctavian is administered. The SoC Cohort will include participants who received prophylactic treatment with any of the following SoC treatments, recombinant or human plasma-derived (PD) blood coagulation FVIII or emicizumab. Participants in the SoC Cohort cannot have a history of exposure to Roctavian. Eligibility criteria will be confirmed at time of enrollment based on DHR field that the participant fulfills the AbD inclusion/exclusion criteria.

7.3.5. Participant Selection

7.3.5.1. Inclusion Criteria

Individuals will be included in the study if they meet all the following criteria on the index date:

- Male PwSHA, as recorded in the DHR
- ≥ 18 years of age at index
- Treatment with Roctavian or SoC hemostatic prophylaxis during the recruitment window
 - Participant administered commercially available Roctavian. Note: Assignment of a therapeutic strategy is not determined by this protocol.
 - OR
 - Has received prophylactic treatment with exogenous FVIII or emicizumab.
- Participant (or their legally authorized representative, if appropriate) have provided written, signed informed consent to participate in this study
 - Note: those identified as participating in the AbD within the DHR are assumed to have provided consent. Actual consent documents will be held at the site and outside of the data extract that would be expected from the DHR.

7.3.5.2. Exclusion Criteria

Individuals will be excluded from the study if they meet any of the following criteria on the index date:

- Is currently in, or previously participated (in the last 12 months before index), an interventional clinical trial involving an investigational product to treat HA
- History of inhibitors against FVIII ever (or current) as recorded in the DHR prior to index
- Presence of acute infections (such as acute respiratory infections or acute hepatitis) or uncontrolled chronic infections (such as chronic active hepatitis B), and/or known significant hepatic fibrosis or cirrhosis at index

7.3.5.3. Inclusion/Exclusion Criteria Variables

Table 2 outlines the variables and operational definitions of the inclusion/exclusion criteria.

Table 2: Inclusion/Exclusion Criteria Variables

Variable	Captured in DHR	DHR data field name	Operational definition/description
Clinical trial participation	Yes	
 • Participation in clinical trial • Current participation in clinical trial • Name of the clinical trial 	
 • In the last 12 months before index • No (exclude participant if yes) • Clinical trial name (free text field) to be utilized to specifically exclude interventional trials, if feasible; If not feasible, any clinical trial will be excluded • Participation in AbD and/or non-interventional studies of Roctavian will not result in exclusion • Exclusion criteria confirmed at time of enrollment based on DHR field confirming that the participant fulfills the AbD inclusion/exclusion criteria
History of Inhibitors (ever)	Yes	
 • Diagnosis • Inhibitor tests against FVIII/FIX positive in this reporting period • Occasion • Positive/negative result 	
 • Yes/No • Based on any recording of the DHR variables for inhibitors developed before the participant started treatment at

Variable	Captured in DHR	DHR data field name	Operational definition/description
			
the current treatment center, positive inhibitor tests after enrollment in the DHR, or use of immune tolerance therapy (ITT)
 
 Exclusion will be based upon either 2 positive inhibitor tests (regardless of occurrence before or after enrollment in DHR) or 1 positive inhibitor tests (regardless of occurrence before or after enrollment in DHR) and use of ITT Use of ITT will be identified if occasion = "ITT" Exclusion criteria additionally confirmed at time of enrollment based on DHR field confirming that the participant fulfills the AbD inclusion/exclusion criteria.
Severe HA	Yes	
 Diagnosis Hemophilia severity 	
 Severe (exclude participant if moderate, mild, or subclinical) Inclusion criteria additionally confirmed at time of enrollment based on DHR field confirming that the participant fulfills the AbD inclusion/exclusion criteria
Sex	Yes	
 Gender 	
 Male (exclude participant if female or diverse) Inclusion criteria additionally confirmed at time of enrollment

Variable	Captured in DHR	DHR data field name	Operational definition/description
			based on DHR field confirming that the participant fulfills the AbD inclusion/exclusion criteria
Age	Yes (calculated)	
 Year of birth¹ 	
 Age at Index Date ≥18 years Confirmed at time of enrollment based on DHR field confirming that the participant fulfills the AbD inclusion/exclusion criteria
Treatment with prophylaxis inclusion	Yes	
 Preparation/ medicinal product Gene therapy 	
 Participants who are administered Roctavian or SoC medication as recorded in the DHR For Roctavian Cohort, gene therapy drug = "Roctavian" For SoC Cohort, participant has received any prophylactic treatment with exogenous FVIII or emicizumab Index SoC drug listed for Eds >50 with date of treatment closest to (but not after) the index date; SoC drug must be listed in Table 4 Confirmed at time of enrollment based on DHR field confirming that the participant fulfills the AbD inclusion/exclusion criteria

Abbreviations: AbD: Anwendungsbegleitende Datenerhebung; BU/ml: Bethesda unit/milliliter; DHR: Deutsches Hämophileregister; ED: exposure days; FVIII: coagulation factor VIII; FIX: coagulation factor IX; HA: hemophilia A; ITT: immune tolerant therapy; SoC: standard of care

Note: Data fields in the DHR are either mandatory to be entered into the registry per DHR practices or will be monitored to ensure completeness of data for analyses, however responses may still be unknown.

1. Date of birth (month/year) is collected in DHR, but only year is available for analysis per DHR practices. An assumed day and month of birth (01 July) for all participants will be implemented to describe approximate age of participants at index.

7.4. Variables

The following sections outline all study variables to be used in this study from the DHR. For each variable, the DHR data field name as well as the operational definition and/or description of the variable is outlined. As a note, several variables from the DHR may be outlined to operationalize a variable for use in this study (e.g., dates, event, etc.). All variables planned to be utilized for the analysis *a priori* are defined in sections below. If any changes to these *a priori* definitions occur during the study conduct (for example due to changes to the DHR), these additional variables or definitions will be recorded and described in the interim and final reports. For the purposes of this study, DHR data fields referring to “gene therapy” are referring to Roctavian use.

7.4.1. Baseline Variables

Table 3 includes study variables that will be captured to describe the Roctavian and SoC Cohorts based on data collected on or before their index date, or to be entered at the index date reflecting annual reporting into the DHR for the time period prior to the index date. Measures will be assessed at the most recent time point prior to the index date, unless otherwise specified.

Table 3: Baseline Variables

Variable	Captured in DHR	DHR data field name(s)	Operational definition/description
Unique participant ID	Yes (Derived)	Unique identifier for participants at an HTC are utilized in the DHR. Outputs from the DHR are anonymized, though a consistent study center code and de-identified participant id at that site will be available to identify participants	
 Calculated field based on a de-identified study center code and unique participant code (e.g., participant at study center A may be identified as A-101)
Index date	Yes	
 Patient takes part in data collection during the application? Start of the AbD (date of consent) 	
 ddmmyyy Date of Roctavian administration for Roctavian Cohort Date of study consent for SoC Cohort
Age	Yes (calculated)	
 Year of birth¹ 	
 Age at Index Date (continuous) Age groups: 18-40, 41-64, 65+ Age groups in 5-year increments
Age at HA diagnosis	Yes (calculated)	
 Year of birth¹ Date of diagnosis 	
 Age at HA diagnosis derived from participant’s year of birth and date of diagnosis, unless date of diagnosis is recorded as “unknown” Reported similar to the Age variable above
Age at first FVIII therapy administration	Yes (calculated)	
 Year of birth¹ Date of the first factor administration 	
 Age at first FVIII therapy administration derived from participant’s year of birth and date of first FVIII administration, unless date of administration is recorded as “unknown”

Variable	Captured in DHR	DHR data field name(s)	Operational definition/description
HTC	--		
 Derived from the site associated with study consent and primarily managing a participant De-identified form based on HTC identifier collected in DHR
Height (within 12 months before index date)	Yes	
 Size 	
 Participant height (cm) If a participant is missing a height value(s), the nearest height within 12 months before and after the missing height value will be used
Weight (within 12 months before index date)	Yes	
 Weight 	
 Participant weight (kg) If a participant is missing a weight value(s), the nearest weight within 12 months before and after the missing weight value will be used
BMI (within 12 months before index date)	Yes (calculated)	
 Weight; Size 	
 Calculated field from weight (kg) and height (cm) variables $(\text{kg}/\text{m}^2)^{14}$ 
 <18.50 (underweight) 18.50 - <25.00 (normal range) 25.00 - <30.00 (overweight/pre-obesity) ≥ 30.00 (obese) Categories may be categorized as dichotomous variable (e.g., obese vs. not)
Family history of hemophilia at time of diagnosis (ever)	Yes	
 Family has a history of hemophilia at the time of diagnosis 	
 Yes No Unknown
History of exposure to HCV infection (ever)	Yes	
 Status HCV infection Cured infection – date of the first findings with this result Active infection – date of the last findings with this result Eradication treatment carried out 	
 Not specified No infection (anti-HCV negative) Cured infection Active infection Presence of acute or uncontrolled chronic hepatic infections at index is an exclusion criterion, which will be confirmed at time of enrollment. HCV status as documented in the DHR will be used to describe the population as well as confirm inclusion/exclusion criteria. Exclusion criteria will additionally confirmed at time of enrollment based on DHR field confirming that the participant fulfills the AbD inclusion/exclusion criteria.
History of chronic liver disease (ever)	Yes	
 Liver disease status Date liver fibrosis (new diagnosis) 	
 Not specified Liver fibrosis (new diagnosis) Liver fibrosis (chronic) Liver cirrhosis child A² Liver cirrhosis child B Liver cirrhosis child C Liver failure Categories may be categorized as dichotomous variable (e.g., yes or no)

Variable	Captured in DHR	DHR data field name(s)	Operational definition/description
			
 Presence of known significant hepatic fibrosis or cirrhosis at index is an exclusion criterion, which will be confirmed at time of enrollment based on DHR field confirming that the participant fulfills the AbD inclusion/exclusion criteria.
Other comorbidities	Yes	
 Other diseases 	
 Prespecified list of comorbid diseases including: 
 Malignancy: expected to be defined consistently with the safety outcomes Hypertension is sustained elevation of resting systolic blood pressure (≥ 130 mm Hg), diastolic blood pressure (≥ 80 mm Hg), or both¹⁵ Osteoporosis is a progressive metabolic bone disease that decreases bone mineral density (bone mass per unit volume), with deterioration of bone structure. It is defined as DXA results for T-scores $\leq -2.5$¹⁶
Von Willebrand factor	Yes		
 Measured in IU/mL
Target joints	Yes	
 Localization Bleeding location 	
 Yes/No If localization = "target joint", then target joints will = "yes" Number and location of target joints will be based on location (shoulder, elbow, hip, knee, ankle joint, or other joint) and side (left, right, not applicable, or unknown) of bleeds identified as "target joint" For example, if target joint bleeds are recorded at the same location on both sides (e.g., a target joint bleed at the left ankle and a separate target joint bleed at the right ankle), this will be counted as 2 separate target joints. If the target joint location is "other joint" or the side of bleeding is "not applicable or unknown", the number of target joints identified from the bleed will be counted as 1 target joint.
AAV5 antibody status (ever)	Yes	
 Have you been tested for AAV antibodies? If yes: tested serotype If yes: date If yes: result (positive/negative) 	
 Derived from AAV testing for AAV5 being conducted and result of positive/negative
Prophylaxis type	Yes	
 Preparation/ medicinal product 	
 FVIII only Non-factor products only (e.g., Emicizumab) FVIII and non-factor products See Table 4 for drug classifications

Variable	Captured in DHR	DHR data field name(s)	Operational definition/description
Use of immunosuppression (ever)	Yes	
 Was immunosuppression performed due to the gene therapy If yes: drug type immunosuppression 	
 For participants in Roctavian Cohort, was immunosuppression used (yes/no) Immunosuppressant drugs based on the DHR specified list of immunosuppressant medications
FVIII infusion rate (before index date)	Yes (calculated)	
 Preparation/ medicinal product Frequency Start of reporting period End of reporting period 	
 Number of FVIII infusions during 12-month baseline period Infusion rate will be derived based on the therapy usage and frequency of individual usage periods recorded in the DHR for any reason Data is expected to be able to allow for summaries of AIR To be calculated for FVIII separately (by class) from emicizumab Calculate annualized metric of the number of infusions by dividing the number of infusions by the number of days in the relevant time period, multiplied by 365.25
Prior FVIII utilization (before index date)	Yes (calculated)	
 Occasion Preparation/ medicinal product Consumption/ delivered Weight Start of reporting period End of reporting period 	
 Total IU during the baseline period and annual utilization of FVIII concentrates expressed as IU/kg/year Total IUs received over the 12 months before index date divided by the weight (kg) closest to index date, stratified by occasion of use: bleed (spontaneous hemorrhage), prophylaxis, short-term prophylaxis (intensified on-demand treatment), surgery, ITT, other/unknown Calculate annualized metric of the FVIII usage multiplied by an individualized factor based on amount of prior history (e.g., if 26 weeks of history, multiply by 2), stratified by occasion of use: bleed (spontaneous hemorrhage), prophylaxis, short-term prophylaxis (intensified on-demand treatment), surgery, ITT, other/unknown
SoC class switching	Yes (calculated)	
 Occasion Preparation/ medicinal product Therapy start End of therapy Start of reporting period End of reporting period 	
 Participants who switched between SoC treatments during the 12 months prior to index date (SHL to EHL; SHL to emicizumab; EHL to emicizumab [and vice-versa]; PD to emicizumab). Participants will be considered to have a switch if occasion = "prophylaxis" for ≥ 2 different medicinal products identified as SoC treatment classes in Table 4 with therapy dates that do not overlap
Prior ABR (before index date)	Yes (calculated)	
 Occasion Therapy scheme Severity Localization 	
 Using the most recent 12 months of pre-index data (when available), calculate ABR using number of prior bleeds within the reporting period start and stop dates

Variable	Captured in DHR	DHR data field name(s)	Operational definition/description
		
 Start of reporting period End of reporting period 	
 Note: a bleeding event is captured if occasion for therapy is spontaneous bleeding/hemorrhage (regardless of severity) Calculate annualized metric of the number of bleeding events multiplied by an individualized factor based on amount of prior history (e.g., if 26 weeks of history, multiply by 2) ABR will be reported as total ABR, treated ABR (therapy scheme = "on-demand"), major ABR (severity = "severe" or "life-threatening"), life-threatening ABR (severity = "life-threatening"), and joint ABR (localization = "joint") See further details in Table 5 for bleed definitions

Abbreviations: AAV: adeno-associated virus; ABR: annualized bleeding rate; AIR: annualized infusion/injection rate; BMI: body mass index; cm: centimeter; DHR: Deutsches Hämophileregister; DXA: dual-energy X-ray absorptiometry; FVIII: coagulation factor VIII; HA: hemophilia A; HCV: hepatitis C virus; HTC: hemophilia treatment center; ITT: immune tolerant therapy; IU: international units; kg: kilogram; mm HG: millimeter of mercury; SoC: standard of care

Note: Data fields in the DHR are either mandatory to be entered into the registry per DHR practices or will be monitored to ensure completeness of data for analyses, however responses may still be unknown.

- Date of birth (month/year) is collected in DHR, but only year is available for analysis per DHR practices. An assumed day and month of birth (01 July) for all participants will be implemented to describe approximate age of participants at index.
- Progression of fibrosis or cirrhosis will be identified based on recording of an increased Child-Turcotte-Pugh classification (e.g., A → B, B → C) of liver disease relative to liver disease status at baseline or the new diagnosis of cirrhosis.¹⁷⁻¹⁹

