Variable	Found by literature review	From previous PS work	Clinical expert opinion	Considerations
Baseline/prior bleeding history (e.g., ABR)	✓	✓	✓	Include regardless of statistical association, based on clinical relevance
Baseline FVIII utilization	✓	✓	✓	Include based on statistical association and correlation with other variables (e.g., baseline/prior bleeding history and baseline prophylaxis class)
Baseline prophylaxis class (FVIII vs. emicizumab)	✓	✓	✓	Include based on statistical association and correlation with other variables (e.g., baseline/prior bleeding history and FVIII utilization)
Age	✓	✓	✓	Include based on statistical association
Height, Weight and/or BMI	✓	✓	✓	Include based on statistical association
Baseline von Willebrand factor (IU/mL)	✓	X	✓	Include based on statistical association
Number of target joints	✓	✓	X	To be considered depending on statistical association and correlation with other variables (e.g., baseline/prior bleeding history and joint health score)
Joint health (e.g., baseline/prior HJHS)	X	X	✓	To be considered depending on statistical association and correlation with other variables (e.g., baseline/prior bleeding history and number of target joints)
Baseline/prior type of bleeds	X	X	✓	To be considered depending on statistical association and correlation with other variables (e.g., baseline/prior bleeding history and target joints)
Geography (HTC/site/region/country)	✓	✓	X	Site to be considered depending on statistical association and correlation with other variables
Prophylaxis class switching (e.g., SHL/PD to EHL/emicizumab)	✓	✓	X	To be considered depending on statistical association and correlation with other variables
Baseline/prior pain (e.g., BPI-sf)	X	X	✓	To be considered depending on statistical association and correlation with other variables (e.g., target joints and HJHS)

Variable	Found by literature review	From previous PS work	Clinical expert opinion	Considerations
Baseline/prior QoL (e.g., haemo-QoL-A)	X	X	✓	To be considered depending on statistical association and correlation with other variables
Activity status	X	X	✓	Not considered as this there is no validated questionnaire for lifestyle factors in PwSHA
Baseline/prior history of liver fibrosis/cirrhosis	✓	X	X	Significant liver fibrosis/cirrhosis is accounted for by the exclusion criteria, but less severe liver fibrosis to be considered based on statistical association

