7.9.2. Analysis of Baseline Characteristics

Descriptive analysis will be conducted to describe baseline demographic and clinical characteristics of the Roctavian and SoC Cohorts. See Table 3 for a list of all variables that will be described for the two Cohorts. The baseline characteristics will capture data before the index date.

Measures of central tendency and dispersion (mean, SD, median) will be calculated and reported for continuous variables for each Cohort. Continuous variables may be categorized into intervals, with the distribution of participants (n, %) provided. Independent sample t-tests for mean values and Wilcoxon rank-sum tests for median values will be performed as a comparison between the Roctavian and SoC Cohorts.

For categorical variables, distributions and frequencies will be compiled and reported. Data will include the frequency (n, %) of total participants observed in each category. Chi-square tests will be performed as a comparison between the Roctavian and SoC Cohorts.

SMD will be calculated for both continuous and categorical variables. SMD represents a commonly used statistic to examine the balance of covariate distribution between groups, with a value greater than 0.1 indicating some imbalance between groups, and SMDs >0.25 indicating poor balance.⁴⁵

Participant characteristics will be presented for all participants prior to weighting and after weighting (for Roctavian and SoC Cohorts separately), overall, and for subgroups and sensitivity analyses where appropriate. Participant characteristics prior to and after weighting will be compared using the statistical tests noted above to capture differences between the observed population and the weighted target population.

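### The fill rule for missing baseline weight in SAP Table 3 does not stop at index, so a weight recorded after Roctavian infusion can reach propensity-score candidates

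*Protocol*

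**What the plan says.** SAP 7.4.1 introduces Table 3 as describing the cohorts "based on data collected on or before their index date", or from annual reports entered at index that cover the time before it. It adds: "Measures will be assessed at the most recent time point prior to the index date, unless otherwise specified". SAP 7.9.2 repeats the limit: "The baseline characteristics will capture data before the index date".

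The weight row in Table 3 carries the same window in its label, "Weight (within 12 months before index date". Its operational definition then says that if a weight is missing, "the nearest weight within 12 months before and after the missing weight value will be used". The height row has the matching rule, "the nearest height within 12 months before and after the missing height value will be used", and BMI is calculated from the two.

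Further down Table 3, baseline factor VIII use is the total IU over the 12 months before index "divided by the weight (kg) closest to index date". No direction is given.

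SAP Table 6 (Section 7.8.2.1) lists "Height, Weight and/or BMI" and baseline factor VIII utilization as potential propensity-score variables, and SAP 7.8.1 says every variable in that table will be assessed as a candidate. SAP 7.3.2 sets index at the infusion date for the Roctavian Cohort and at the consent date for the SoC Cohort.

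**The concern.** The propensity score models who receives Roctavian, so its covariates have to be fixed before treatment. A weight taken after infusion is not. If weight changes after infusion, for whatever reason, a later weight carries that change into a variable presented as baseline, and the weighting then treats it as a pre-existing difference to be removed.

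The two cohorts are also not alike here. After index, a Roctavian participant has been infused and may be receiving immunosuppression (protocol Table 5). A SoC participant has only given consent. Protocol 7.2.4 keeps the Table 5 variables out of the propensity score; the fill rule leaves an indirect route for their consequences through weight. At stake are the weight and BMI rows of the balance table, baseline IU/kg, and whatever part of these the score retains.

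**Working it through.** The plan states no figure on this point, so the check is of timing and scale.

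**1. Which rule governs.** The section rule, the row label and SAP 7.9.2 all point to data before index. The section rule, however, applies only where nothing else is specified, and the weight row does specify something else. On the text, the fill rule prevails over the general limit, and it conflicts with its own row label.

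**2. How far it reaches.** The 12 months run from the missing value, not from index. For a missing value dated m months before index, the donor weight may lie from −(m + 12) to (12 − m) months relative to index:

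- m = 0: −12 to +12
- m = 3: −15 to +9
- m = 6: −18 to +6
- m = 9: −21 to +3
- m = 12: −24 to 0

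The latest admissible donor is therefore 12 months after index, when the missing value is the one at index. If missing means that the 12-month look-back holds no weight at all, a value dated at index has no donor in the backward half of the window, so the rule can only supply a later one.

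**3. With the window closed at index.** The latest donor is month 0 for every m above, and no post-infusion weight can enter.

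**4. Effect on baseline IU/kg.** If the weight used differs from the true baseline weight by a fraction g, IU/kg changes by 1/(1 + g) − 1. The values of g are assumptions; the documents give none.

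- g = −5%: 1/0.95 − 1 = +5.3%
- g = +2%: 1/1.02 − 1 = −2.0%
- g = +5%: 1/1.05 − 1 = −4.8%
- g = +10%: 1/1.10 − 1 = −9.1%

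These are changes for one affected participant. The effect on a cohort mean is diluted by the share of participants affected.

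**5. Who is affected.** For weight and BMI, only participants without a usable weight on or before index. For IU/kg the group may be wider: if closest to index is read in both directions, a weight taken 10 days after index displaces one taken two months before, although nothing is missing.

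**The case against.** The strongest reply is that the situation should rarely arise where it matters. Only in the Roctavian Cohort is a later weight post-treatment. SAP Table 4 gives the Roctavian dose per kg of body weight, so a weight should exist at infusion. Protocol Table 2 schedules height and weight both before and at index. Protocol 7.1 makes the fields mandatory for participants, with completeness monitored, and protocol 10.2 expects minimal missing data. This stands, and it limits the size of the problem.

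A second reply is that the two-sided fill was meant for serial weights. Protocol Table 3 lists weight for follow-up as well as baseline, SAP 7.4.2 refers back to SAP Table 3 for weight details, and follow-up IU/kg uses an average weight. That is plausible, but the row does not say so: it stands in the baseline table under a baseline label, without that restriction.

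A reader might go further and infer that the rule will produce a visible false imbalance. The shift in the standardized mean difference for weight is the share filled × mean change ÷ SD. Assuming an SD of 15 kg, 10–40% filled after index and a 3–8 kg mean change in one cohort only, it runs from 0.10 × 3/15 = 0.02 to 0.40 × 8/15 = 0.21, and meets the 0.1 marker of SAP 7.8.2.3 at 0.30 × 5/15 = 0.10. The documents do not support these inputs: none of them appears there, the shares filled conflict with the expected completeness, and nothing states that gene therapy or immunosuppression changes weight. At 5% filled even an 8 kg change gives 0.05 × 8/15 = 0.03. The largest of these values is below the 0.25 at which SAP 7.8.2.3 requires the model to be refined.

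**Conclusion.** The point holds as a contradiction in a stated rule. The baseline weight row is labelled as pre-index but is filled from either side of it, and the IU/kg row leaves the direction open. A post-infusion weight can therefore reach variables that are candidates for the propensity score.

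It would go too far to say that such a weight does enter the score. Weight or BMI and factor VIII use are kept only on statistical association and, for factor VIII use, on correlation with other variables. Nor do the documents show that the primary comparison would be biased to any material degree. The effect is zero if every participant has a weight on or before index and closest is read as looking backward only, or if weight does not change after index. It is probably small in any case, and its size cannot be derived from the documents. Adult height raises no practical concern. The reason to change the rule is that a propensity score should not admit post-treatment values and that closing the gap costs very little.

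**What to change.** In SAP Table 3, define baseline weight, and the weight used for BMI, as the last weight recorded on or before index, and bar later values. Say the same in the factor VIII utilization row, so that the weight closest to index means the closest one on or before it. Keep the two-sided fill for follow-up weights only, and label it so. Adult height may come from any date.

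Send what remains missing to the multiple imputation in SAP 7.9.5.1. That section must be reconciled at the same time: it plans multiple imputation for propensity-score covariates with less than 40% missing, then says that apart from birth month no other fields will be imputed. If the second statement governed, SAP 7.8.1 would give no propensity score to a participant lacking a retained covariate.

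The cost is a few sentences in the SAP and slightly more missing baseline weights to impute. The sample size does not change. Protocol 10.3 has the SAP finalized before the data cut for the 18-month interim analysis, so the change belongs before then.
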